5.1. Inclusion Criteria

Participants are eligible to be included in the study only if all the following criteria apply:

1. Can give signed informed consent/assent which includes compliance with the requirements and restrictions listed in the ICF and in this protocol
2. At least eighteen (18) years of age at the time of signing the informed consent.
3. Histologically confirmed locally advanced or metastatic or locally advanced/unresectable urothelial carcinoma (including renal pelvis, ureter, urinary bladder, urethra). Mixed histologies are acceptable provided transitional cell carcinoma is the predominant histology.
 - a) Measurable disease per RECIST v1.1 criteria.
 - b) Experienced disease progression or recurrence either (1) following platinum-containing chemotherapy for metastatic or locally advanced/unresectable urothelial cancer or (2) within 12 months from completion of neo-adjuvant or adjuvant platinum-containing chemotherapy for localized muscle-invasive urothelial cancer.
4. Able to provide, a tumor tissue sample collected during screening and prior to administration of bintrafusp alfa (see Study Reference Manual [SRM] for details). See Section [4.5](#)
5. Able to provide an archival tumor sample (preferably from the most recent biopsy). Archival material is formalin fixed tumor tissue sample from a biopsy of a tumor lesion. See SRM and Section [8.11.2](#) for further details on tumor tissue requirements.
6. Eastern Cooperative Oncology Group (ECOG) performance status (PS) 0-1. See [Appendix 10](#).
7. Adequate organ system functions as defined by the laboratory assessments listed in [Appendix 2](#).

System	Laboratory Values
Hematologic^a	
ANC	$\geq 1.5 \times 10^9/L$
Hemoglobin	$\geq 9 \text{ g/dL}$
Platelets	$\geq 100 \times 10^9/L$
INR or PT ^b	$\leq 1.5 \times \text{ULN}$
Hepatic	
Albumin	$\geq 2.5 \text{ g/dL}$
ALT and AST	$\leq 2.5 \times \text{ULN}$ or $\leq 5 \times \text{ULN}$ for participants with documented liver metastases
Total bilirubin	Bilirubin $\leq 1.5 \times \text{ULN}$ (isolated bilirubin $> 1.5 \times \text{ULN}$ is acceptable if bilirubin is fractionated and direct bilirubin $< 35\%$)
Renal	
Calculated CrCl ^c	$\geq 30 \text{ mL/min}$
Cardiac	
Ejection Fraction ^d	$\geq 50\%$

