8.1. Screening Assessments

All screening assessments must be performed within 45 days prior to the first dose unless otherwise specified. Screening scans for lesion assessments are required within 28 days of the first dose. The ICF may be signed within 45 days prior to enrollment; tumor tissue biopsy procedure must be performed during the screening period after participant ICF obtained. An archived tumor sample is mandatory and will be used for PD-L1 testing.

The term 'baseline' refers to the assessment performed during the screening period prior to first dose of study treatment that serves as a comparison or control. For example, the baseline laboratory assessment is the laboratory assessment performed prior to first dose.

Refer to [Table 1](#) for additional details on assessments required at Screening and prior to the start of study intervention.

The following assessments are required during screening:

- Informed Consent
- Demographic parameters such as year of birth and sex will be captured
- Medical history including cardiovascular medical history, tobacco use, prior use of probiotics and antibiotics within (60 of first dose) and other risk factors will be assessed as related to the inclusion/exclusion criteria.
- Complete physical examination.

- Skin assessments are performed at Baseline on all participants (refer to [Table 1](#) and [Section 8.4.1](#)). A detailed medical history of genetic or iatrogenic dermatologic conditions, skin type, geographical location, occupational or environmental exposure to radiation or chemicals will be queried.
- Disease characteristics including medical, surgical, and treatment history (best response to prior therapy [radiotherapy and systemic] will be recorded), date of initial diagnosis, primary tumor location, stage at initial diagnosis, histology, and current sites of disease will be taken as part of the disease history/status. In addition, molecular characterization of cancer, including PD-L1 expression by IHC will be recorded. If PD-L1 expression has been previously determined, results and type of assay utilized (e.g., Ventana SP263, Ventana SP142, Dako 28-8, or Dako 22C3) must be recorded in eCRF.
- A brain CT/MRT scan performed as clinically indicated.
- ECOG Performance Status.
- Vital Signs (refer to [Section 8.4.3](#)).
- Concomitant medication
 - Recorded starting from screening through post-study treatment follow-up.

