10.6. Appendix 6: Liver Safety: Required Actions and Follow-up Assessments

Phase I/II liver chemistry stopping and increased monitoring criteria have been designed to assure participant safety and evaluate liver event etiology (in alignment with the FDA premarketing clinical liver safety guidance).

<http://www.fda.gov/downloads/Drugs/GuidanceComplianceRegulatoryInformation/Guidances/UCM174090.pdf>.

Phase I/II Liver Chemistry Stopping Criteria and Required Follow up Assessments

Liver Chemistry Stopping Criteria – Liver Stopping Event Including participants with documented liver metastases/tumor infiltration at baseline AND entry criteria ALT >2.5 x ULN but ≤5 x ULN	
ALT-absolute	Both ALT ≥5 x ULN and ≥2 x baseline value
ALT Increase	Both ALT ≥3 x ULN and ≥1.5 x baseline value that persists for ≥4 weeks
Bilirubin^{1,2}	ALT ≥3 x ULN and bilirubin ≥2 x ULN (>35% direct bilirubin)
INR²	ALT ≥3 x ULN and INR >1.5, if INR measured
Cannot Monitor	Both ALT ≥3 x ULN and ≥1.5 x baseline value that cannot be monitored for 4 weeks
Symptomatic³	Both ALT ≥3 x ULN and ≥1.5 x baseline value associated with symptoms (new or worsening) believed to be related to liver injury or hypersensitivity
Required Actions and Follow up Assessments following ANY Liver Stopping Event	
Actions	

 • Immediately discontinue study treatment • Report the event to GSK within 24 hours • Complete the CRF within one week of occurrence and complete an SAE data collection tool if the event also meets the criteria for an SAE² • Perform liver event follow up assessments • Monitor the participant until liver chemistries resolve, stabilize, or return to within baseline (see MONITORING below) • Do not restart/rechallenge participant • If restart/rechallenge not allowed per protocol or not granted, permanently 	
 • Viral hepatitis serology⁴ • Obtain INR and recheck with each liver chemistry assessment until the transaminases values show downward trend. • Only in those with underlying chronic hepatitis B at study entry (identified by positive hepatitis B surface antigen) quantitative hepatitis B DNA and hepatitis delta antibody⁵. • Blood sample for pharmacokinetic (PK) analysis, obtained approximately 48hrs after last dose⁶ • Serum creatine phosphokinase (CPK) and lactate dehydrogenase (LDH). • Fractionate bilirubin, if total bilirubin ≥2xULN

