
Participant with entry criteria ALT $\leq 2.5 \times$ ULN
 
ALT $\geq 3 \times$ ULN but $< 5 \times$ ULN and bilirubin $< 2 \times$ ULN, without symptoms believed to be related to liver injury or hypersensitivity and who can be monitored weekly for 4 weeks
 
Participant with documented liver metastases/tumor infiltration at baseline AND entry criteria ALT $> 2.5 \times$ ULN but $\leq 5 \times$ ULN
 
ALT $\geq 3 \times$ ULN and 1.5 x baseline value but ALT $< 5 \times$ ULN and 2 x baseline value and bilirubin $< 2 \times$ ULN, without symptoms believed to be related to liver injury, or hypersensitivity and who can be monitored weekly for 4 weeks
	
 Notify the GSK medical monitor within 24 hours of learning of the abnormality to discuss participant safety. Participant must return weekly for repeat liver chemistries (ALT, AST, alkaline phosphatase, bilirubin) until they resolve, stabilize or return to within baseline If at any time participant meets the liver chemistry stopping criteria, proceed as described above 
For participants with entry criteria ALT $\leq 2.5 \times$ ULN
 
 If, after 4 weeks of monitoring, ALT $< 3 \times$ ULN and bilirubin $< 2 \times$ ULN, monitor participants twice monthly until liver chemistries normalize or return to within baseline. 
For participants with documented liver metastases/tumor infiltration at baseline AND entry criteria ALT $> 2.5 \times$ ULN but $\leq 5 \times$ ULN
 
 If, after 4 weeks of monitoring, ALT $< 3 \times$ ULN and $< 1.5 \times$ baseline value, and bilirubin $< 2 \times$ ULN, monitor participants twice monthly until liver chemistries normalize or return to within baseline

Reference:

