2.0 GI Toxicities	
	
 - ALT $\geq 3 \times$ ULN and cannot be monitored weekly for 4 weeks 
In the absence of criteria above, hold ICPi temporarily. Consider corticosteroid 0.5-1 mg/kg/d prednisone or equivalent if the abnormal elevation persists. Increase frequency of monitoring. See Appendix 6 for additional details.
 
May resume ICPi treatment followed by taper only when symptoms improve to G1 or less and corticosteroid ≤ 10 mg/d; taper over at least 1 month
 
Participants should be advised to stop unnecessary medications and any known hepatotoxic drugs.
 
Infliximab might not be the most appropriate treatment option in the situation of immune-mediated hepatitis given the potential risk of idiosyncratic liver failure (Note: No clear evidence shows the liver toxicity from infliximab from other studies)
 
Participants should be advised to stop unnecessary medications and any known hepatotoxic drugs

G3: Symptomatic liver dysfunction, fibrosis by biopsy, compensated cirrhosis, reactivation of chronic hepatitis (AST or ALT 5-20 x ULN and/or total bilirubin 3-10 x ULN). For participants with metastatic disease to liver and elevated transaminases at baseline, see Appendix 6 for grading that accommodates baseline liver chemistry values.	
Permanently discontinue ICPi
 
Immediately start corticosteroid 1-2 mg/kg methylprednisolone or equivalent
 
If corticosteroid refractory or no improvement after 3 days, consider mycophenolate mofetil or azathioprine (if using azathioprine should test for thiopurine methyltransferase deficiency)
 
Laboratories at daily or every other day; consider inpatient monitoring for patients with AST/ALT $> 8 \times$ ULN and/or elevated TB 3 x ULN
 
Increase frequency of monitoring to every 1-2 days
 
Infliximab might not be the most appropriate treatment option in the situation of immune-mediated hepatitis given the potential risk of liver failure (Note: No clear evidence shows that the liver toxicity from infliximab from other studies); alternatives include non-TNF-a agents as systemic immunosuppressants If no improvement is achieved with corticosteroids or for patients on combination therapy with a novel agent, with standard chemotherapy, or with targeted therapy, refer to hepatologist for further pathologic evaluation of hepatitis
 
Corticosteroid taper can be attempted around 4-6 weeks; re-escalate if needed; optimal duration unclear

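### Appendix 6 liver rules: for participants with liver metastases and entry ALT above 2.5 × ULN, the increased-monitoring row and the absolute ALT stop do not meet, and the monitoring row cannot be met once baseline reaches 10/3 × ULN

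*Protocol*

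**What the plan says.** Protocol Section 5.1 caps entry ALT at 2.5 × ULN, raised to 5 × ULN "for participants with documented liver metastases". Section 8.1 fixes the reference value: "The term 'baseline' refers to the assessment performed during the screening period prior to first dose".

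Appendix 6 (Section 10.6) then gives two sets of criteria.

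- **Stopping.** The table expressly includes participants with documented "liver metastases/tumor infiltration at baseline AND entry criteria ALT >2.5 x ULN but ≤5 x ULN". Its absolute ALT row is "Both ALT ≥5 x ULN and ≥2 x baseline value". Its persistence row is "Both ALT ≥3 x ULN and ≥1.5 x baseline value that persists for ≥4 weeks". Further rows stop treatment from the same 3 × ULN and 1.5 × baseline level if ALT cannot be followed for 4 weeks, or if liver or hypersensitivity symptoms accompany it. Two more apply from 3 × ULN when bilirubin or INR is also raised.
- **Increased monitoring with continued therapy.** For entry ALT up to 2.5 × ULN, the row runs from 3 to below 5 × ULN. For the liver-metastasis group, the lower limit is 3 × "ULN and 1.5 x baseline value but ALT", and the upper limit is below 5 × "ULN and 2 x baseline value and bilirubin" below 2 × ULN. Meeting a monitoring row brings weekly liver chemistry and notice to the medical monitor within 24 hours.

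For liver-metastasis participants with raised baseline transaminases, the hepatitis part of Appendix 9 (Table A2) says "see Appendix 6 for grading that accommodates baseline liver chemistry values". Appendix 6 contains no grades, only the criteria above.

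**The concern.** The two sets of criteria read as a ladder: closer follow-up on treatment, then stopping. For entry ALT up to 2.5 × ULN the rungs meet, because monitoring ends and the absolute stop begins at 5 × ULN. In the liver-metastasis row, the upper limit keeps a fixed 5 × ULN while the lower limit and the stop scale with baseline. As baseline rises, the monitoring band shrinks and then disappears, and the absolute stop moves further away.

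The affected people are those with the most abnormal eligible liver tests. A stated safety trigger cannot fire for part of the range the protocol admits, and two sites could act differently on the same result. After Week 13 the Schedule of Activities calls for chemistry only every 4 weeks, so whether the weekly row applies makes a practical difference.

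**Working it through.** **Inputs.** Let b be baseline ALT in multiples of ULN, with 2.5 < b ≤ 5 (Sections 5.1 and 10.6). I take the inequality sign on each ULN multiple to carry over to the baseline multiple joined to it, and both joined conditions to be required. The plan gives no figure of its own to reproduce.

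**Step 1: the two rows as written (× ULN).**
- Monitoring: from max(3, 1.5b) to below min(5, 2b).
- Absolute stop: from max(5, 2b) upwards.

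**Step 2: simplify.** Since b > 2.5, 1.5b > 3.75 and 2b > 5. Monitoring becomes 1.5b to below 5, and the absolute stop becomes 2b upwards. Within this group, the 2 × baseline limit in the monitoring row and the 5 × ULN limit in the stop never bind.

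**Step 3: when monitoring is empty.** This happens when 1.5b ≥ 5, that is b ≥ 5/1.5 = 10/3 ≈ 3.33. It covers (5 − 10/3)/(5 − 2.5) = 1.667/2.5 = two thirds of the width of this group's entry range. That is a share of the range, not of participants.

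**Step 4: what lies between the rows.** ALT at or above the row's own lower trigger (1.5b), not below 5 and not yet at 2b, is the interval from max(5, 1.5b) to below 2b.

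| b | Monitoring as written | Absolute stop from | In neither row | Width |
|---|---|---|---|---|
| 2.75 | 4.125 to <5 | 5.5 | 5 to <5.5 | 0.5 |
| 3 | 4.5 to <5 | 6 | 5 to <6 | 1 |
| 10/3 | empty | 6.67 | 5 to <6.67 | 1.67 |
| 4 | empty (≥6 and <5) | 8 | 6 to <8 | 2 |
| 5 | empty (≥7.5 and <5) | 10 | 7.5 to <10 | 2.5 |

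**Step 5: comparison group.** For b ≤ 2.5, 2b ≤ 5, so the absolute stop starts at 5 and monitoring covers 3 to <5. There is no gap.

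**Step 6: the alternative reading.** If the upper limit means that the two thresholds are not both reached, monitoring runs from 1.5b to below 2b: 4.5 to <6 at b = 3, 6 to <8 at b = 4, 7.5 to <10 at b = 5. The rows then meet for every b.

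**The case against.** **The literal reading is strained.** Under it, two of the four limits do no work in this group (Step 2). The row describes continued therapy and uses the same two thresholds as the absolute stop, so reading it as everything short of that stop gives each term a function and removes the gap. This stands as evidence of what was probably meant. It does not settle the matter, because the row joins its upper limits with a plain conjunction and nothing in Appendix 6 says that reaching only one of them keeps a participant under monitoring.

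**Other safeguards apply.** This stands in full. A reader might infer that participants in the gap are unprotected, or that only the monitoring row requires repeat tests. The documents do not support either. From 1.5 × baseline, the persistence, cannot-monitor and symptom stops operate, and the cannot-monitor row itself presupposes four weeks of follow-up. The bilirubin and INR stops operate from 3 × ULN. Table A2 asks for liver tests before each infusion and/or weekly for Grade 1 elevations, and infusions are every 2 weeks. Section 8.4.5 asks for clinically significant, treatment-related abnormal results to be repeated. Section 7.1.2 requires discontinuation when the investigator judges it in the participant's best interest.

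**The gap does not always start at 5 × ULN.** A reader might infer that everything from 5 × ULN to 2 × baseline is uncovered. Above b = 10/3, ALT between 5 × ULN and 1.5 × baseline is below the row's own lower trigger. At b = 5, that reading would count an unchanged ALT as a gap.

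**Figure 2 may resolve it.** Section 7.1.2 presents Figure 2 as the algorithm that includes this group. It is not reproduced in the text available, so it can be neither relied on nor called faulty.

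**Reach is limited.** Enrollment has ceased with 25 participants treated, and the documents do not say whether any had liver metastases with entry ALT above 2.5 × ULN. After the data cut-off, participants are managed under local standard of care. However, Sections 6.10 and 8.2 still make continued treatment conditional on not meeting protocol discontinuation criteria, so the stopping wording keeps its force.

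**Conclusion.** The inconsistency is real but narrow. As written, for liver-metastasis participants with entry ALT above 2.5 and up to 5 × ULN, increased monitoring cannot be triggered from a baseline of 10/3 × ULN. Across the whole group, an ALT band just below the absolute stop, 2.5 × ULN wide at the highest eligible baseline, triggers neither the weekly monitoring and 24-hour notice nor that stop.

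This rests on three assumptions: both joined upper limits are required, baseline equals the entry-range value, and Figure 2 does not say otherwise. It is a contradiction between two rows of one safety appendix, with several other protections still in place. It does not show that anyone went without follow-up. The number affected is unknown and may be small or zero.

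**What to change.** Reconcile the liver-metastasis monitoring row with the absolute-stop row in Appendix 6 so that they meet for every eligible baseline ALT. State in words whether the upper limit means that either threshold, or both, have not been reached. Check Figure 2 against the reconciled text. The sponsor's clinical team sets the limits; none is proposed here.

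The cost is one clarified line in Appendix 6, sent to sites with participants still on treatment. No statistical analysis changes.

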10.7. Appendix 7: Country-specific requirements

There are no country specific requirements.

10.8. Appendix 8: Abbreviations and Trademarks

Abbreviations

CCI	
ADR	Adverse Drug Reaction
AE	Adverse Event
ALT	Alanine Aminotransferase
ANC	Absolute Neutrophil Count
AST	Aspartate Aminotransferase
ASCO	The American Society of Clinical Oncology
β -hCG	Beta-human Chorionic Gonadotropin
CCI	
CI	Confidence Interval
CNS	Central Nervous System
CR	Complete Response
CrCl	Creatinine Clearance
CRP	C Reactive Protein
CSR	Clinical Study Report
CT	Computed Tomography
CTLA-4	Cytotoxic T-Lymphocyte-Associated Protein 4
CCI	
cSCC	cutaneous Squamous-cell Carcinoma
CV	Cardiovascular
DCO	Data Cut-off
CCI	
ECHO	Echocardiogram
ECI	Events of Clinical Interest
ECOG	Eastern Cooperative Oncology Group
eCRF	electronic Case Report Form
EU	European Union
FDA	Food and Drug Administration
FDG-PET	Fluorodeoxyglucose Positron Emission Tomography
FTIH	First-Time-in-Human
GI	Gastrointestinal
GSK	GlaxoSmithKline
Hgb	Hemoglobin
HRT	Hormone Replacement Therapy
Hypothesis	H
IB	Investigator's Brochure
ICF	Informed Consent Form
ICH	International Council on Harmonization of Technical Requirements for Registration of Pharmaceuticals for Human Use

CCI	
IEC	Independent Ethics Committees
CCI	
Ig	Immunoglobulin
CCI	
IL	Interleukin
INR	International Normalized Ratio
irAE	Immune-related Adverse Event
IRB	Institutional Review Board
IRR	Infusion-related Reaction
IV	Intravenous
KA	Keratoacanthoma
kg	Kilogram(s)
LVEF	Left Ventricular Ejection Fraction
mAb	Monoclonal Antibody
MedDRA	Medical Dictionary for Regulatory Activities
MIIBC	Muscle-Invasive Bladder Cancer
µg	Microgram(s)
mg	Milligram(s)
mL	Milliliter(s)
MRI	Magnetic Resonance Imaging
MSDS	Material Safety Data Sheet
MSEC	Millisecond(s)
MUGA	Multigated Acquisition Scan
NCI-CTCAE v5	National Cancer Institute - Common Terminology Criteria for Adverse Events, version 5
ORR	Overall Response Rate
CCI	
CCI	
PD	Progressive Disease
PD-1	Programmed Death 1
PD-L1	Programmed Death-Ligand 1
CCI	
CCI	
PR	Partial Response
PS	Performance Status
PV	Pharmacovigilance
Q2W	Every 2 Weeks
Q3W	Every 3 Weeks
Q6W	Every 6 Weeks
Q12W	Every 12 Weeks
QTc	QT interval duration corrected
QTcF	QT interval duration corrected by Fredericia formula
RAP	Reporting and Analysis Plan
RECIST	Response Evaluation Criteria in Solid Tumors
CCI	

RP2D	Recommended Phase 2 Dose
SCC	Squamous-cell Carcinoma
SD	Stable Disease
SoA	Schedule of Activities
SRM	Study Reference Manual
TCR	T Cell Receptor
TGF- β	Transforming Growth Factor β
TEAE	Treatment Emergent Adverse Event
TNF α	Tumor Necrosis Factor, alpha
TSH	Thyroid Stimulating Hormone
ULN	Upper Limit of Normal
US	United States
WOCBP	Woman of Childbearing Potential

Trademark Information

Trademarks of the GlaxoSmithKline group of companies
NONE

Trademarks not owned by the GlaxoSmithKline group of companies
Bavencio

10.9. Appendix 9: The Recommendations for irAE Management, in Accordance with the Joint American Society of Clinical Oncology Clinical Practice Guidelines and National Comprehensive Cancer Network

Adapted from:

Management of Immune-Related Adverse Events in Patients Treated With Immune Checkpoint Inhibitor Therapy: American Society of Clinical Oncology Clinical Practice Guideline [Brahmer, 2018].

Table of Tables

Table A1	Management of Skin irAEs in Patients Treated With ICPis.....	107
Table A2	Management of GI irAEs in Patients Treated With ICPis	113
Table A3	Management of Lung irAEs in Patients Treated with ICPis.....	118
Table A4	Management of Endocrine irAEs in Patients Treated with ICPis.....	120
Table A5	Management of Musculoskeletal irAEs in Patients Treated With ICPis	126
Table A6	Management of Renal irAEs in Patients Treated With ICPis	130
Table A7	Management of Nervous System irAEs in Patients Treated With ICPis	132
Table A8	Management of Hematologic irAEs in Patients Treated With ICPis	138
Table A9	Management of Cardiovascular irAEs in Patients Treated With ICPis	145
Table A10	Management of Ocular irAEs in Patients Treated With ICPis	148

Table A1**Management of Skin irAEs in Patients Treated With ICPis**

1.0 Skin Toxicities	
1.1 Rash/inflammatory dermatitis	

Definition: Erythema multiforme minor (a targetoid reaction in the skin and mucous membranes usually triggered by infections, such as herpes simplex viruses, but can be associated with an immune-related drug eruption and if progresses to erythema multiforme major, it can be a harbinger of SCAR, such as SJS), lichenoid (resembling the flat-topped, polygonal, and sometimes scaly or hypertrophic lesions of lichen-planus), eczematous (inflammatory dermatitis characterized by pruritic, erythematous, scaly, or crusted papules or plaques on the skin, which is vulnerable to superinfection, psoriasiform [resembling the well-demarcated, erythematous, and scaly papules and plaques of psoriasis], morbilliform [a nonpustular, nonbullosus measles-like exanthematous rash of the skin often referred to as “maculopapular” and without systemic symptoms or laboratory abnormalities, excluding occasional isolated peripheral eosinophilia, palmoplantar erythrodysesthesia [hand-foot syndrome; redness, numbness, burning, itching, and superficial desquamation of the palms and soles], neutrophilic dermatoses [eg, Sweet syndrome], and others]
	
Diagnostic work-up	

Pertinent history and physical examination
 
Rule out any other etiology of the skin problem, such as an infection, an effect of another drug, or a skin condition linked to another systemic disease or unrelated primary skin disorder
 
If needed, a biologic checkup, including a blood cell count and liver and kidney tests
 
Directed serologic studies if an autoimmune condition is suspected, such as lupus or dermatomyositis: a screening antinuclear antibody test, SS-A/Anti-Ro, SS-B/Anti-La if predominantly photodistributed/photosensitivity, antihistone, double-stranded DNA, and other relevant serologies.
 
Consider expanding serologic studies or diagnostic work-up if other autoimmune conditions are considered based on signs, symptoms Skin biopsy
 
Consider clinical monitoring with use of serial clinical photography
 
Review full list of patient medications to rule out other drug-induced cause for photosensitivity
	
Grading	Management
Grading according to CTCAE is a challenge for skin. Instead, severity may be based on BSA, tolerability, morbidity, and duration.	
G1: Symptoms do not affect the quality of life or controlled with topical regimen and/or oral antipruritic	
Continue ICPi
 
Treat with topical emollients and/or mild-moderate potency topical corticosteroids
 
Counsel patients to avoid skin irritants and sun exposure

G2: Inflammatory reaction that affects quality of life and requires intervention based on diagnosis	
Consider holding ICPi and monitor weekly for improvement. If not resolved, interrupt treatment until skin AE has reverted to Grade 1
 
Consider initiating prednisone (or equivalent) at dosing 1 mg/kg, tapering over at least 4 weeks
 
In addition, treat with topical emollients, oral antihistamines, and medium- to high-potency topical corticosteroids

G3: As G2 but with failure to respond to indicated interventions for a G 2 dermatitis	
Hold ICPi therapy and consult with dermatology to determine appropriateness of resuming
 
Treat with topical emollients, oral antihistamines, and high-potency topical corticosteroids
 
Initiate (methyl)prednisolone (or equivalent) 1-2 mg/kg, tapering over at least 4 weeks

